8.3. Participant Withdrawal Criteria

8.3.1. Withdrawal of Participants

Participants are free to withdraw from the study at any time without giving reasons. Furthermore, the investigator may withdraw a participant for reasons such as intolerance to study treatment, intercurrent illness, need for medication that is contraindicated, significant noncompliance with the requirements of the study, or withdrawal of consent. The investigator will assess the reasons for withdrawal as far as possible and will fully record the circumstances and medical details.

Participants who permanently discontinue study treatment and who do not withdraw from the study will be asked to return to the clinic for all remaining study treatment visits and participate in all follow-up assessments according to the visit schedule.

8.3.2. Individual Stopping Criteria

Participants will be permanently discontinued from study treatment in the event of:

- Anaphylactic reaction to study treatment
- Treatment with any prohibited concomitant medication or procedure (Section 9.2.2)
- Diagnosis of a malignancy during study, excluding carcinoma in situ of the cervix or squamous or basal cell carcinoma of the skin
- Evidence of pregnancy
- Any infection that:
 - Requires parenteral treatment with antibiotic, antifungal, antiviral, anti-parasitic, or anti-protozoal agent
 - Requires oral treatment with such agents for longer than 2 weeks
 - Is opportunistic, such as tuberculosis and other infections whose nature or course may suggest an immunocompromised status
- Severe laboratory abnormalities, such as:
 - Neutrophil count $<0.5 \times 10^3/\mu\text{L}$
 - Platelet count $<50 \times 10^3/\mu\text{L}$
 - ALT and/or AST values $>3 \times \text{ULN}$ with total bilirubin $>2 \times \text{ULN}$, excluding confirmed Gilbert's Syndrome
- Confirmed AST and/or ALT $>5 \times \text{ULN}$ (for more than 2 weeks)
- Other reasons that may lead to the permanent discontinuation of study treatment include:

- Certain AEs deemed related to the study treatment (eg, severe and prolonged injection site reactions) or study procedures

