7.9. Schedule of Events

The visit schedule is presented in Table 3.

Table 3: Study RVL0 121-04 Schedule of Events

Procedures	Screening Period	Prior to Rand	Rand/ Baseline	Treatment Period				End of Study/ Final Safety	Notes
Visit	V-1	V0	V1	V2	V3	V4	V5	V6	
Week	-6	-	0	1	2	4	6	8	
Day	-	-	0	7	14	28	42	56	
Window	≤ 6 weeks	-	-	± 3 days	± 3 days	± 3 days	± 3 days	± 3 days	
Screening/ Baseline									
Informed consent	X	-	-	-	-	-	-	-	-
Demographics/ Medical history review	X	-	-	-	-	-	-	-	-
Inclusion/exclusion criteria review	X	X	X	-	-	-	-	-	
Treatment									
Randomization IWRs	-	-	X	-	-	-	-	-	
Administer study treatment	-	-	DBL	DBL	DBL	-	-	-	Pharmacy site staff will be unblinded to prepare the treatment. Investigators, study staff members, and study participants will be blinded to the treatment and dose level (4 mg or 8 mg or placebo) and will remain blinded throughout the study.
Efficacy	X	X	-	-	-	-	-	-	Daily completion of the DSQ starts on the first day it is issued to the participant.
DSQ training and issue handset	X	X	-	-	-	-	-	-	

Procedures	Screening Period	Prior to Rand	Rand/ Baseline	Treatment Period				End of Study/ Final Safety	Notes
Visit	V -1	V0	V1	V2	V3	V4	V5	V6	
Week	-6	-	0	1	2	4	6	8	
Day	-	-	0	7	14	28	42	56	
Window	≤ 6 weeks	-	-	± 3 days	± 3 days	± 3 days	± 3 days	± 3 days	
DSQ compliance assessment	-	-	X	X	X	X	X	X	
Retrieval of DSQ handset	-	-	-	-	-	-	-	X	
Esophageal endoscopy and biopsy with EoE-EREF5	EGD	-	-	-	-	X			-
EoEHSS - histology scoring	X	-	-	-	-	X			-
PGI-S	-	-	X	-	X	X	X	X	
PGI-C	-	-	-	-	X	X	X	X	
Safety									
Physical examination	X	-	X	X	X	X	X	X	Predose on Day 0.
ECG	X	-	X	X	X	X	X	X	
Height	X	-	-	-	-	-	-	-	
Weight	X	-	X	X	X	X	X	X	
Vitals	X	-	X	X	X	X	X	X	Should be measured within 15 minutes prior to dosing, and +15 minutes (+/- 5 minutes) postdose on Days 0, 7, and 14.
Diet history	X	X	X	X	X	X	X	X	
Concomitant medications and procedures	X	X	X	X	X	X	X	X	
Review of adverse events	-	X	X	X	X	X	X	X	

Procedures	Screening Period	Prior to Rand	Rand/ Baseline	Treatment Period				End of Study/ Final Safety	Notes
Visit	V -1	V0	V1	V2	V3	V4	V5	V6	
Week	-6	-	0	1	2	4	6	8	
Day	-	-	0	7	14	28	42	56	
Window	≤ 6 weeks	-	-	± 3 days	± 3 days	± 3 days	± 3 days	± 3 days	
Local laboratory									
Hematology and serum chemistry	X	-	X	X	X	X	X	X	
Coagulation	X	-	X	X	X	X	X	X	Should be performed before the procedure of endoscopy with esophageal biopsies on days the procedure is performed.
Urinalysis	X	-	X	X	X	X	X	X	
Serology	X	-	-	-	-	-	-	-	

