16. The following treatments within 3 months before the screening visit, or any condition that, in the opinion of the investigator, is likely to require such treatment(s) during the study:
Systemic immunosuppressive/immunomodulating drugs (eg, omalizumab, cyclosporine, mycophenolate-mofetil, interferon [IFN] γ , Janus kinase inhibitors, azathioprine, methotrexate, and other biologics that are ongoing [eg, dupilumab, benralizumab, mepolizumab, or vedolizumab]).
17. Diagnosed with active parasitic infection; or suspected parasitic infection, unless clinical and (if necessary) laboratory assessments have ruled out active infection before randomization.
18. Chronic or acute infection requiring treatment with systemic antibiotics, antivirals, or antifungals within 1 month prior to screening.

19. Use of oral antibiotics/anti-infectives within 2 weeks prior to screening.
20. Known or suspected immunosuppression, including history of invasive opportunistic infections (eg, tuberculosis, non-tuberculous mycobacterial infections, histoplasmosis, listeriosis, coccidioidomycosis, pneumocystosis, aspergillosis) despite infection resolution, or otherwise recurrent infections of abnormal frequency, or prolonged infections suggesting an immunocompromised status, as judged by the investigator.
21. Known history of human immunodeficiency virus (HIV) infection.
22. Positive or indeterminate hepatitis B surface antigen (HBsAg) or hepatitis C antibody at screening.
23. Moderate or severe renal impairment (eGFR <60 mL/min/1.73 m²) or end stage renal disease.
24. Elevated transaminases (alanine aminotransferase [ALT] and/or aspartate aminotransferase [AST]) > 3 times the upper limit of normal (ULN) at screening.
25. History of malignancy within 5 years prior to screening, except completely treated in situ carcinoma of the cervix and completely treated and resolved nonmetastatic squamous or basal cell carcinoma of the skin.

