8.3.3. Allowable Deviations in Timing of Study Treatment

Study treatment dosing may be delayed around the allowable 3-day windows as specified in the Schedule for Events, for any reason, such as:

- Clinically important laboratory abnormalities, such as:
 - Neutrophil count $<1.0 \times 10^3/\mu\text{L}$ but $>0.5 \times 10^3/\mu\text{L}$
 - Platelet count $<100 \times 10^3/\mu\text{L}$ but $>50 \times 10^3/\mu\text{L}$
 - Creatine phosphokinase (CPK) $>10 \text{ ULN}$
- Short-term, self-limiting conditions (eg, infections resolving spontaneously or requiring <2 weeks of oral anti-infective treatment), with the exception of upper respiratory infections
- Other intercurrent illnesses

A decision to delay study treatment should be discussed with the medical monitor. The investigator may delay study treatment at any time, even without consultation with the medical monitor if the urgency of the situation requires immediate action and if this is determined to be in the participant's best interest. However, the medical monitor should be contacted as soon as possible in any case of study treatment delay.

A participant is not allowed to skip any doses of study treatment during the study.

Dose reductions are not allowed.

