9. TREATMENT OF PARTICIPANTS

9.1. Description of Study Treatment

Study treatment will be administered as a repeat-dose regimen of IRL201104 4 mg or 8 mg or placebo on Days 0, 7, and 14 (3 total doses over 14 days).

Study treatment will be delivered by IV bolus via a cannula over 30 seconds, and not to exceed 60 seconds.

An overview of the investigational product used in the study is provided in [Table 4](#).

Table 4: Investigational Product

Investigational Product			
Product Name:	IRL201104		Placebo
Dosage Form:	Lyophilized cake reconstituted with sterile water for injection	Lyophilized cake reconstituted with sterile water for injection	Lyophilized cake reconstituted with sterile water for injection
Unit Dose	4 mg (0.8 mg/ml per 20 mL vial reconstituted with 20 mL)	8 mg (0.8 mg/ml per 20 mL vial reconstituted with 10 mL)	N/A
Volume Required for Reconstitution	20 mL	10 mL	10 mL
Volume for Administration	10 mL	10 mL	10 mL
Route of Administration	IV injection	IV injection	IV injection

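### On scheduled visits, the isolated-transaminase stopping criterion (above 5 x ULN, lasting more than 2 weeks) cannot be met before the last dose for an on-treatment rise

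*Protocol*

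**What the plan says.** Protocol Section 8.3.2 opens its mandatory list with "Participants will be permanently discontinued from study treatment in the event of". Two entries are hepatic:

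- ALT and/or AST above 3 x ULN together with total bilirubin above 2 x ULN, "excluding confirmed Gilbert's Syndrome". This one has no duration condition.
- Confirmed AST and/or ALT above 5 x ULN, with no bilirubin condition, provided that it lasts "for more than 2 weeks".

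Section 9.1 places all treatment "on Days 0, 7, and 14 (3 total doses over 14 days". Table 3 (Section 7.9) allows ±3 days at the Day 7 and Day 14 visits. Its row "Hematology and serum chemistry" is marked at screening and at Days 0, 7, 14, 28, 42 and 56.

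Section 8.3.3 covers delays: "Study treatment dosing may be delayed around the allowable 3-day windows as specified in the Schedule for Events". Its example laboratory reasons are neutrophils, platelets and CPK; transaminases are not among them. It adds: "A participant is not allowed to skip any doses of study treatment during the study".

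Exclusion criterion 24 in Section 8.2 bars entry for "Elevated transaminases (alanine aminotransferase [ALT] and/or aspartate aminotransferase [AST]) > 3 times the upper limit of normal (ULN) at screening". A later value above 5 x ULN is therefore a rise since screening.

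**The concern.** The only effect of a Section 8.3.2 criterion is to withhold doses not yet given. A duration condition longer than the time between first detection and the last dose removes that effect. The isolated-transaminase criterion asks for more than 14 days, while the nominal dosing period is exactly 14 days and the first scheduled post-dose sample falls halfway through it.

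At stake is what a site does with a marked rise and normal bilirubin at Day 7, when up to two doses are still due. As an illustration, ALT of 8 x ULN with normal bilirubin would meet neither numerical hepatic criterion at that visit and is not among the named reasons for delay. The site must then rely on judgement, in a protocol that appears to have a specific rule for the case.

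**Working it through.** This is day arithmetic; no power or sample-size formula applies.

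**Inputs (Protocol)**
- Duration required: more than 14 days (8.3.2).
- Doses: Days 0, 7 and 14 (9.1).
- Visit windows from Table 3: Day 0 has none; Day 7 ±3 = Days 4 to 10; Day 14 ±3 = Days 11 to 17; Day 28 ±3 = Days 25 to 31.
- Chemistry at each of these visits (Table 3). SAP Section 7.8 lists chemistry only at screening and Days 0, 7 and 56. The check uses the fuller schedule in Table 3, which is also the schedule in the SAP's own Table 1.

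**The plan's own figure.** Nominal dosing span = 14 − 0 = 14 days, as Section 9.1 states. With the window, the third dose can fall as late as 14 + 3 = Day 17.

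**Longest documented rise before the third dose.** Duration = day of later visit − day of first abnormal sample. The shortest is the earliest later visit minus the latest first sample; the longest is the reverse.

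| First abnormal sample | Later visit | Nominal | Shortest | Longest | Day pairs above 14 |
|---|---|---|---|---|---|
| Day 7 visit | Day 14 visit (dose 3) | 14 − 7 = 7 | 11 − 10 = 1 | 17 − 4 = 13 | 0 of 49 |
| Day 7 visit | Day 28 visit | 28 − 7 = 21 | 25 − 10 = 15 | 31 − 4 = 27 | 49 of 49 |
| Day 14 visit | Day 28 visit | 28 − 14 = 14 | 25 − 17 = 8 | 31 − 11 = 20 | 21 of 49 |
| Day 0 visit | Day 14 visit (dose 3) | 14 − 0 = 14 | 11 − 0 = 11 | 17 − 0 = 17 | third dose on Day 15, 16 or 17 |

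Each window has 7 days, so two windowed visits give 7 × 7 = 49 day pairs. These are counts of possible schedules, not probabilities.

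**Earliest trigger for an on-treatment rise.** The first whole day more than 14 days after Day 4 is 4 + 15 = Day 19, which is later than Day 17. On scheduled visits, a rise found at Day 7 is first documented as lasting long enough at the Day 28 visit, when no dose is left. A rise first seen at Day 14 is nominally exactly 14 days old at Day 28, so it does not yet qualify.

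**Where the criterion could still act**
- A Day 0 value already above 5 x ULN, with the third dose on Days 15 to 17. This is a baseline value, not an on-treatment rise.
- An unscheduled sample no later than Day 17 − 15 = Day 2 for a third dose on Day 17, or Day 16 − 15 = Day 1 for one on Day 16.
- A third dose delayed beyond its window, if Section 8.3.3 permits that.

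**The case against.** The strongest reply is that the protocol does not depend on this criterion. Several other routes are open for a marked isolated rise at Day 7:

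- The bilirubin-linked criterion has no duration and can stop a dose whenever bilirubin is also raised.
- The severe laboratory abnormalities in 8.3.2 are given as examples, so an unlisted severe value can fall within that mandate. The section also allows stopping for certain treatment-related AEs.
- Section 8.3.3 lets the investigator delay dosing whatever the reason, and at any time when urgent. It speaks of delay around the windows and sets no clear outer limit.
- Section 8.3.1 allows the investigator to withdraw a participant, and Section 7.7 provides IDMC safety review.
- Section 12.5 requires significantly abnormal tests to be repeated, and the medical monitor to be consulted when an abnormality neither resolves nor is explained. Unscheduled samples are therefore expected.

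All of this stands, and it limits the point. It does not remove it. These routes rest on judgement or consultation, or need a second abnormality. The one numerical rule written for an isolated rise carries an explicit duration, and a site could read that as saying that a shorter rise need not stop treatment.

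A reader might go further and treat exclusion criterion 24 as a contradiction, because 3 x ULN bars entry while 5 x ULN does not at once stop dosing. The documents do not support that: an entry limit and an on-treatment stopping limit serve different purposes and may differ.

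A reader might also infer that uneven use of discretion makes discontinuations non-comparable across arms. Randomization is central (9.3) and investigators are blinded (9.3.1), so differences between sites have no evident route to becoming differences between arms. Consistency between sites is the most that can be said to suffer.

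**Conclusion.** The duration condition in 8.3.2 is inconsistent with the dosing and laboratory schedules. For a rise first seen at the first scheduled post-dose chemistry, the longest documented duration before the third dose is 13 days against more than 14 required, and the earliest trigger, Day 19, is 2 days after the latest in-window third dose. On scheduled visits the criterion can stop none of the doses for an on-treatment rise.

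This rests on Table 3 visit days and windows, on duration counted from the first abnormal sample, and on no dosing beyond the window.

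It would be tempting to conclude that the criterion never applies, or that the trial has no working hepatic stop. Neither follows. The Day 0, early unscheduled-sample and long-delay cases can satisfy the criterion, the bilirubin-linked criterion works as written, and discretionary stopping remains. The documents also report no significant AEs for single doses up to 8 mg (Section 5.3), and a Day 7 finding bears on at most two doses. The gap is in one mandatory numerical trigger: worth correcting by amendment, but not a gap in every means of protecting a participant.

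**What to change.** The sponsor, with the medical monitor and the IDMC, should reconcile four things: the duration condition in 8.3.2, the dosing schedule in 9.1, the laboratory schedule in Table 3, and the delay list and no-skip sentence in 8.3.3. The protocol should then state one consistent action for a marked isolated transaminase rise seen while doses remain. Which passage changes, and the threshold, duration and action, are clinical decisions for them; none is proposed here.

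The cost is amendment wording. ALT and AST are already scheduled at every dosing visit, so no new visit is implied. If the agreed action depends on a result from the same visit, Table 3 would also have to say when the sample is taken and read relative to the dose, which its chemistry row does not do now. Depending on how the passages are reconciled, a few more participants may stop treatment early. Under Section 8.3.1, those who remain in the study are still asked to attend all remaining visits and follow-up assessments.

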8.3.3. Allowable Deviations in Timing of Study Treatment

Study treatment dosing may be delayed around the allowable 3-day windows as specified in the Schedule for Events, for any reason, such as:

- Clinically important laboratory abnormalities, such as:
 - Neutrophil count $<1.0 \times 10^3/\mu\text{L}$ but $>0.5 \times 10^3/\mu\text{L}$
 - Platelet count $<100 \times 10^3/\mu\text{L}$ but $>50 \times 10^3/\mu\text{L}$
 - Creatine phosphokinase (CPK) $>10 \text{ ULN}$
- Short-term, self-limiting conditions (eg, infections resolving spontaneously or requiring <2 weeks of oral anti-infective treatment), with the exception of upper respiratory infections
- Other intercurrent illnesses

A decision to delay study treatment should be discussed with the medical monitor. The investigator may delay study treatment at any time, even without consultation with the medical monitor if the urgency of the situation requires immediate action and if this is determined to be in the participant's best interest. However, the medical monitor should be contacted as soon as possible in any case of study treatment delay.

A participant is not allowed to skip any doses of study treatment during the study.

Dose reductions are not allowed.

8.3.4. Replacement of Participants

Participants who discontinue from the study will be replaced if they did not receive 3 doses of study treatment and the final endoscopy as randomized.

9. TREATMENT OF PARTICIPANTS

9.1. Description of Study Treatment

Study treatment will be administered as a repeat-dose regimen of IRL201104 4 mg or 8 mg or placebo on Days 0, 7, and 14 (3 total doses over 14 days).

Study treatment will be delivered by IV bolus via a cannula over 30 seconds, and not to exceed 60 seconds.

An overview of the investigational product used in the study is provided in [Table 4](#).

Table 4: Investigational Product

Investigational Product			
Product Name:	IRL201104		Placebo
Dosage Form:	Lyophilized cake reconstituted with sterile water for injection	Lyophilized cake reconstituted with sterile water for injection	Lyophilized cake reconstituted with sterile water for injection
Unit Dose	4 mg (0.8 mg/ml per 20 mL vial reconstituted with 20 mL)	8 mg (0.8 mg/ml per 20 mL vial reconstituted with 10 mL)	N/A
Volume Required for Reconstitution	20 mL	10 mL	10 mL
Volume for Administration	10 mL	10 mL	10 mL
Route of Administration	IV injection	IV injection	IV injection

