28. Treatment with a live (attenuated) vaccine within 3 months prior to screening and/or treatment of a killed vaccine within 30 days prior to screening, until the end of the study with the exception of a coronavirus disease of 2019 (COVID-19) vaccine, as described in Section 9.2.1.
29. Pregnant or breastfeeding women, or women planning to become pregnant or breastfeed during the study.
30. Women unwilling to use adequate birth control, if of reproductive potential* and sexually active. Adequate birth control is defined as agreement to consistently practice an effective and accepted method of contraception throughout the duration of the study and for 30 days after the last dose of study treatment. These include: hormonal contraceptives, intrauterine device, or double barrier contraception (ie, condom and diaphragm), or male partner with documented vasectomy.

*For females, menopause is defined as at least 12 consecutive months without menses; to include laboratory confirmation of post-menopausal status (ie, a follicle stimulating hormone (FSH) of 2.25 U/mL must be documented). Hysterectomy, bilateral oophorectomy, or bilateral tubal ligation must be documented, as applicable; if documented, women with these conditions are not required to use additional contraception.

Investigational product, dosage, and mode of administration:

IRL201104 and placebo is supplied as a sterile, lyophilized cake in a standard glass vial and is reconstituted with sterile water for injection.

For both the 4 and 8 mg dose levels, the amount of drug substance in each 20 mL vial is 0.8 mg/ml, which is reconstituted with 10-20 mL water for injection (WFI). Investigational product will be administered in a volume of 10 mL.

IRL201104 4 mg and 8 mg and placebo are administered as an IV bolus injection over 30 seconds (not to exceed 60 seconds) on Days 0, 7, and 14 (3 total doses over 14 days).

Pharmacy staff will be unblinded for investigational product preparation. Investigators, study team members and study participants will be blinded to the dose level given (4 mg, 8 mg, or placebo) and will remain blinded throughout the study.

Duration of treatment:

Screening period: up to 6 weeks

Double-blind treatment and follow-up period: 8 weeks

Total study duration: up to 14 weeks

Reference therapy, dosage, and mode of administration:

None

Criteria for Evaluation

Primary Endpoints:

- Change from baseline in the peak esophageal intraepithelial eosinophil count at Week 4.

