Two dose strengths were selected to be tested in the current Phase 2a clinical study: 4 mg and 8 mg. These dose levels have been well tolerated in healthy participant studies to date, the maximum doses studied to date being 8 mg on 7 consecutive days. Experience with anti-IL-5 compounds would indicate that marked and sustained suppression of eosinophils has not been associated with adverse effects for example increased risk of parasitic infection.

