10. STUDY TREATMENT MATERIALS AND MANAGEMENT

10.1. Study Treatment

IRL201104 drug product and placebo is packaged as a sterile, lyophilized cake in a standard glass vial and is reconstituted with sterile water for injection (WFI) ([Table 4](#)). The WFI used to reconstitute the drug product will be an authorized product supplied by the clinical study center.

For both the 4 and 8 mg doses, the amount of drug substance in each 20 mL vial is 0.8 mg/ml, which is reconstituted with 10 or 20 mL WFI. Investigational product will be administered in a volume of 10 mL.

The process for reconstitution will be detailed in the sponsor pharmacy manual.

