10.4. Study Treatment Preparation

Instructions for the preparation and reconstitution of study treatment will be provided in the sponsor pharmacy manual.

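### Does stating the vial strength only as 0.8 mg/mL leave the doses in the two active arms undetermined?

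*Protocol*

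**What the plan says.** Table 4 in Protocol Section 9.1 gives the unit dose of the two active arms as "4 mg (0.8 mg/ml per 20 mL vial reconstituted with 20 mL" and "8 mg (0.8 mg/ml per 20 mL vial reconstituted with 10 mL". It then has a row headed "Volume Required for Reconstitution", with 20 mL for the 4 mg arm and 10 mL for the 8 mg and placebo arms, and a row giving 10 mL as the injected volume in every arm.

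The Synopsis covers both dose levels in one sentence: "the amount of drug substance in each 20 mL vial is 0.8 mg/ml, which is reconstituted with 10-20 mL water for injection (WFI". Section 10.1 says nearly the same, with two fixed volumes in place of a span: "the amount of drug substance in each 20 mL vial is 0.8 mg/ml, which is reconstituted with 10 or 20 mL WFI". It adds: "Investigational product will be administered in a volume of 10 mL". Section 10.4 hands over the practical detail: "Instructions for the preparation and reconstitution of study treatment will be provided in the sponsor pharmacy manual".

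The intended doses of 4 mg and 8 mg appear in the objectives, the arm descriptions, the dose rationale and Table 4.

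**The concern.** A concentration does not say how much of a dry solid is in a vial until a volume is named, and the protocol names none for this purpose. The only volume attached to the vial itself is 20 mL. A reader who multiplies 0.8 mg/mL by 20 mL arrives at double the labelled dose in both arms. A reader who takes 0.8 mg/mL as the strength after reconstitution finds that the two active arms receive the same dose.

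The stakes would be real if either reading reached the pharmacy. Section 7.8.2 describes prior experience as "the maximum doses studied to date being 8 mg on 7 consecutive days", so a 16 mg injection would lie above that level, and the safety margins in Table 2 are computed for 8 mg. Reconstitution volume is also the only thing that separates the two active arms, so the Synopsis's span of 10 to 20 mL looks careless. An ethics committee member or investigator working from the protocol alone has to make an assumption to confirm either dose from the printed strength.

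**Working it through.** **Inputs**
- Labelled doses: 4 mg and 8 mg (Table 4).
- Reconstitution volume V: 20 mL (4 mg arm) and 10 mL (8 mg arm) (Table 4).
- Injected volume: 10 mL in all arms (Table 4, Section 10.1).
- Printed strength: 0.8 mg/mL, with a 20 mL vial (Table 4, Synopsis, Section 10.1).
- Vial content M in mg: not stated.

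**Formula.** Delivered dose = M / V x 10. The 4 mg arm receives M/20 x 10 = M/2 and the 8 mg arm receives M/10 x 10 = M. The ratio of 1 to 2 between arms holds for any M; only the absolute level depends on it.

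**Vial content implied by the labels**
- 4 mg arm: M = 4/10 x 20 = 8 mg.
- 8 mg arm: M = 8/10 x 10 = 8 mg.

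The two arms agree. The printed strength, which was not used in those two lines, gives the same figure when applied to 10 mL: 0.8 x 10 = 8 mg.

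**Four readings of 0.8 mg/mL**

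| Reading | Vial content | 4 mg arm | 8 mg arm | Agrees with both labels |
|---|---|---|---|---|
| Strength at 10 mL reconstitution | 0.8 x 10 = 8 mg | 8/20 x 10 = 4 mg | 8/10 x 10 = 8 mg | Yes |
| Strength over the 20 mL vial | 0.8 x 20 = 16 mg | 16/20 x 10 = 8 mg | 16/10 x 10 = 16 mg | No |
| Strength after reconstitution in both arms | 16 mg and 8 mg, so not one vial | 0.8 x 10 = 8 mg | 0.8 x 10 = 8 mg | No |
| 0.8 mg in the whole vial | 0.8 mg | 0.8/20 x 10 = 0.4 mg | 0.8/10 x 10 = 0.8 mg | No |

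Under the first reading the injected strengths are 8/20 = 0.4 mg/mL and 8/10 = 0.8 mg/mL.

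**The Synopsis span.** Its sentence covers both dose levels together, so 10 to 20 mL can be read as the two ends that Section 10.1 and Table 4 list separately. Table 4 assigns one volume to each arm and leaves no intermediate volume to choose.

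**The case for a change.** The best case for requiring a change is that the back-calculation starts from the labelled doses and so cannot verify them: it shows that an 8 mg vial is compatible with the labels, not that the vial holds 8 mg. The two most direct readings of the printed words, 0.8 mg/mL over 20 mL and 0.8 mg/mL as the final strength, both contradict the unit doses in the same table. Investigators are blinded and only pharmacy staff prepare the product, so few people are placed to notice a misreading, and correcting one table and two sentences would cost little.

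Part of this stands. The strength lacks its reference volume in all three places, and the reading that works is not spelled out. But the circularity is only partial. There is one unknown, two arms that could have disagreed and do not, and a printed strength that gives the same 8 mg when paired with the 10 mL volume beside it in the 8 mg column. The 16 mg figure requires 20 mL to be a fill volume; for a cake in a glass vial that accepts either 10 or 20 mL of water, it can equally be the size of the container. The safety comparison therefore depends on a reading that conflicts with both stated doses. Whether any ambiguity reaches preparation turns on a pharmacy manual that cannot be examined here.

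**Conclusion.** The wording is incomplete, but the arms are not undetermined. The protocol states both doses, gives each arm a fixed reconstitution volume and a fixed injected volume, and admits a reading that reproduces 4 mg and 8 mg exactly. The alternative over the full 20 mL would double both doses to 8 and 16 mg, and the alternative of a common final strength would give 8 mg in each arm; neither agrees with the labels. No dosing error is shown.

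No statistical result is affected either. SAP Section 6.2 labels the groups by their assigned dose, all summaries are descriptive, and none of the planned summaries uses vial content.

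This is a clerical slip of units. The Synopsis, Table 4 and Section 10.1 must be reconciled with each other and with the pharmacy manual, which is a matter of recording detail the sponsor already holds rather than of altering the plan. The conclusion assumes that 20 mL may denote container size and that the manual gives pharmacists an unambiguous procedure; the second cannot be checked from these documents. No view is taken on which vial content or dose is right.
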